5.3. Screening Procedures

5.3.1. Recipient – Screening and Enrollment

Recipients will be screened for potential eligibility for the trial. Those patients who initially appear eligible will have the trial thoroughly explained to them and will be asked for consent for participation.

A recipient will be considered enrolled in the trial only when a matching DCD liver is identified, procured, preserved on OCS and transplanted into a consented eligible recipient. Data will be collected according to the Schedule of Assessments found in [Appendix 1](#).

5.3.2. Donor Liver – Initial Screening, Retrieval and OCS Preservation

The retrieval team will evaluate the donor and the quality and suitability of the liver for transplantation in general and for inclusion in the trial. After final evaluation of the donor liver in the donor's abdomen and upon acceptance into the trial, the investigators will retrieve and preserve the donor liver using the OCS Liver System according to the Instructions for Use.

Data collected that relates to organ retrieval, OCS preservation and assessment will be collected according to the Schedule of Assessments in [Appendix 1](#).

5.3.3. Donor Liver Assessment on OCS Liver System and Acceptance for Transplantation

All donor livers that are preserved on OCS Liver System MUST meet all three conditions of the following clinical criteria to be eligible for transplantation into a recipient:

- DCD Donor livers on OCS Liver System are deemed to be clinically acceptable for transplantation by the Site Principal Investigator based on their clinical judgment and interpretation of OCS Liver System's hemodynamic and metabolic parameters;
- OCS Liver System perfusate lactate levels that are trending down on OCS Liver System from initial sample to final sample taken during OCS Liver perfusion and below 10 mmol/l at the end of OCS perfusion;
- Able to achieve and maintain OCS Liver System perfusion parameters for the organ; mean Hepatic Artery Pressures (HAP), Hepatic Artery Flows (HAF), mean Portal Vein Pressure (PVP) and Portal Vein Flow (PVF) as recommended in the IFU.

Any decision to turn down livers after they have been retrieved, preserved and assessed on OCS™ Liver System should be made by the Site Principal Investigator (or should be made in consultation with the site Principal Investigator), and the clinical reason for turning down the donor liver for transplantation will be documented.

5.4. Enrolled DCD Donor Livers and Recipients

- Recipient Enrollment: for the assessment of post-transplant outcomes, a consented potential recipient will be considered enrolled in the trial when they are transplanted with any DCD donor liver preserved and assessed on OCS Liver System.
- DCD Donor Liver Enrollment: for the assessment of donor liver utilization rate, a DCD donor liver will be considered enrolled in the trial if it meets the eligibility criteria for donor liver inclusion and was instrumented on the OCS Liver System for ex-vivo perfusion and assessment.

6. DATA COLLECTION AND FOLLOW-UP

Data collection will include:

Donor:

- Eligibility information
- Demographics, Medical and Social Histories, Cause of Death
- Liver assessment including warm ischemic time, cross clamp and flush times
- OCS preservation parameters
- OCS liver enzymes and lactate levels
- Device malfunction (if applicable)
- Non-transplant reason(s) (if applicable).

Recipient:

- Eligibility information
- Demographics, Medical History and risk factors
- Transplant details, including documentation of reconstruction of any accessory vessels or anatomical abnormalities prior to perfusion
- Lab assessments:
 - AST – from ICU admission through Day 7 ± 1 day (for hospitalized patients only)
 - Bilirubin – Day 7 ± 1 day (for hospitalized patients only)
 - INR – Day 7 ± 1 day (for hospitalized patients only)
- Subject and graft survival from Day 30 through Month 60. Follow-up at these timepoints may be done via telephone and/or review of the subject's medical record.
- Presence/absence of ischemic cholangiopathy at 6 months
- Liver graft-related serious adverse events up to 30 days post-transplant
- Serious adverse events up to 30 days post-transplant
- Protocol deviations (if applicable).

See the Schedule of Assessments in [Appendix 1](#) for details and time windows for data collection parameters.

7. EVALUATION OF ADVERSE EVENTS

In this trial, only liver graft-related serious adverse events (LGRSAEs) as defined in [Section 7.1](#) below and serious adverse events (SAEs) will be collected through Day 30 post-transplant.

7.1. Evaluation of Liver Graft-Related Serious Adverse Events

Liver Graft-Related Serious Adverse Events are those which have any untoward effect on the health or safety of the patient and that are related to the transplanted liver (except for acute rejection). LGRSAEs will be collected from the time a subject is transplanted with a liver preserved on OCS until the completion of the 30-day follow-up evaluation and will consist only of the following events:

- Primary non-function (defined as irreversible graft dysfunction requiring emergency liver re-transplantation or death, in the absence of immunologic or surgical causes);
- Ischemic biliary complications (ischemic biliary strictures, and non-anastomotic bile duct leaks);
- Vascular complications (non-surgical hepatic artery stenosis, hepatic artery thrombosis and portal vein thrombosis);
- Liver allograft infections (liver abscess, cholangitis).
- Liver graft-related coagulopathy.

All LGRSAEs will be followed until resolution or stabilization of the event.

7.2. Serious Adverse Events (SAEs)

An adverse event will be classified as serious if it meets any of the following criteria:

- Results in, leads to, or contributes to, a death
- Is life-threatening
- Results in permanent disability or incapacity (i.e., permanent impairment of a body function or permanent damage to a body structure)
- Requires in-patient hospitalization or prolongs hospitalization
- Necessitates medical or surgical intervention to preclude a permanent disability or incapacity
- Results in fetal distress, fetal death or a congenital anomaly/birth defect.

7.3. Anticipated Adverse Events

Anticipated adverse events that are related to liver transplantation (and not specific to the OCS device) includes, but is not limited to:

- Acute rejection
- Atrial and ventricular arrhythmias
- Bleeding
- Hemodynamic instability
- Death
- Fever
- Early liver allograft dysfunction (EAD)
- Respiratory failure
- Liver primary non-function
- Bile leaks
- Hepatic artery thrombosis
- Portal vein thrombosis
- Cholangitis
- Liver abscess
- Diaphragmatic injury
- Phrenic nerve injury
- Sepsis
- Renal dysfunction and/or failure
- Hyperammonemia
- Malignancy (post-transplant lymphoproliferative disorder (PTLD))
- Multiple organ failure
- Myocardial infarction
- Neurological dysfunction
- Hepatic dysfunction
- Diabetes due to steroid and anti-rejection medications
- Pancreatitis
- Peptic ulceration
- Gastritis
- Gastro esophageal reflux disease (GERD)
- Aspiration
- Cardiac tamponade
- Pneumo-mediastinum
- Pneumothorax
- Hemothorax
- Ascites
- Pleural effusion
- Venous thromboembolism (deep venous thrombosis [DVT])
- Pulmonary embolism (PE)
- Abdominal wound dehiscence
- Organ deemed not transplantable after retrieval
- Stroke
- Psychosis
- Ileus
- Bowel obstruction
- GI Bleeding (upper or lower)
- Cerebrovascular accident
- Peripheral vascular clotting or occlusion due insertion of mechanical support or equivalent
- Delirium, confusion and neurological complications
- Hepatic coma
- Retransplantation
- Limb gangrene due to vascular occlusion due insertion of mechanical support
- Use of mechanical circulatory support
- Coagulopathy
- Blood product transfusion
- Transfusion reaction
- Hyperacute rejection
- Anastomotic site complications; narrowing, bleeding or occlusion
- Bowel thromboembolic complications and gangrene
- Protamine and other anti-heparin medication reaction
- Heparin induced thrombocytopenia.

7.4. Unanticipated Adverse Device Effect (UADE)

An UADE is any serious adverse effect on health or safety or any life-threatening problem or death caused by, or associated with, a device, if that effect, problem, or death was not previously identified or encountered before at least once in standard clinical practice, in nature, severity, or degree of incidence in the investigational plan or application (including a supplementary plan or application), or any other unanticipated serious problem associated with a device that relates to the rights, safety, or welfare of subjects.

Unanticipated adverse device effects (UADE) should be reported to TransMedics, Inc., preferably within 48 hours of the time the investigator learns of the event, but in no case later than 5 working days.

7.5. Recording and Reporting of Adverse Event

All LGRSAEs and SAEs will be collected through 30 days post-transplant and should be entered as soon as possible into the study database. For all LGRSAEs and SAEs, the investigator may be asked to supply any additional source documents that may be deemed necessary by the Sponsor.

7.5.1. Relationship of an LGRSAE or SAE to OCS Liver

The investigator will assess the relationship of the event to the OCS method of preservation. The relationship will be assessed using the following categories:

- **Definitely Related:** There is a reasonable causal and temporal relationship between preservation with the OCS™ Liver and the adverse event.
- **Probably Related:** It is more likely than not that there is a reasonable causal relationship between preservation with the OCS™ Liver and the adverse event.
- **Unlikely Related:** There is a temporal relationship with preservation with the OCS™ Liver and the adverse event, but there is not a reasonable causal relationship between the trial device and the event.
- **Unrelated:** There is no relationship between preservation with the OCS™ Liver and the adverse event.

The investigator will rate the severity of the adverse event using the following categories:

- **Mild:** The adverse event is transient and/or easily tolerated by the subject.
- **Moderate:** The adverse event causes the subject discomfort and interrupts the subject's usual activities.
- **Severe:** The adverse event causes considerable interference with the subject's usual activities.

7.6. Pre-Existing Conditions

Pre-existing diseases or conditions will not be reported as adverse events.

8. STATISTICAL METHODS

8.1. General

Continuous variables will be summarized using descriptive statistics, specifically the mean, median, standard deviation, minimum, and maximum. Categorical variables will be summarized using frequencies and percentage.

All statistical procedures will be performed using SAS Version 9.3 or higher.

8.2. Analysis Populations

Data analysis and summarization will be performed using the analysis populations defined below.

8.2.1. Per Protocol Population

The Per Protocol (PP) population will consist of all subjects who are transplanted in the study with a liver preserved on OCS Liver System and have no major protocol deviations. The PP population will be used for primary analysis of effectiveness.

8.2.2. Modified Intent-to-Treat Population

The modified Intent-to-Treat (mITT) population will include subjects who are transplanted in the study with a liver preserved on OCS Liver System. The mITT population will be used for the sensitivity analysis of effectiveness. The safety analysis will also be based on the mITT population.

8.2.3. Donor Liver Population

The Donor Liver Population will consist of all donor livers eligible for the study that were instrumented on the OCS. The Donor Liver Population will be used for rate of donor liver utilization after OCS Liver perfusion.

8.3. Data Analysis

The statistical analysis plan (SAP) provides details on the statistical methods planned for this study and will be finalized prior to the database lock. Statistical summaries described in the sections below will primarily be provided for all subjects (i.e., overall summary) in the analysis populations of interest unless otherwise stated.

8.3.1. Subject Disposition

Subject disposition will be summarized and presented for the number and percentage of subjects who were enrolled, screen failures, completed the study, and discontinued early (including reasons for discontinuations).

8.3.2. Major Protocol Deviations

Major protocol deviations will be identified and documented based on a review of potential deviations. The potential major protocol deviations will be identified before database lock, either through programmatic checks of study data (e.g., inclusion/exclusion criteria violations),

as well as through review of selected data listings (e.g., site-entered comments). The potential major protocol deviations to be reviewed include, but are not limited to, subjects who did not meet inclusion/exclusion criteria or eligibility was not adequately verified.

Individual major protocol deviations will be presented in a data listing. The number and percentage of subjects with major protocol deviations will be summarized by the type of deviations.

8.3.3. Demographics and Baseline Characteristics

Demographics, including (age, gender, race, and ethnicity where applicable), and other baseline characteristics collected at screening, such as height, weight, body mass index will be summarized using descriptive statistics. These data will be presented as a listing.

8.3.4. Effectiveness Analysis

8.3.4.1. Primary Endpoint

The primary endpoint for this study is Liver Graft Survival through 6 months post-transplant, as defined per UNOS data collection criteria for Graft Status after liver transplantation*.

* If patient dies and the death was a result of some other factor unrelated to graft failure, the graft will be considered functioning not failed (https://unos.org/wp-content/uploads/unos/Adult_TRF_Liver.pdf).

The primary effectiveness endpoint will show that the 6-month graft survival rate meets a performance goal defined as 0.765 (76.5%). This OPG was determined based on the 2019 SRTR/OPTN annual data report showing that 6-month graft survival for the recipients of DCD livers is 88.5%, with an 12% margin to allow for the fact that extended warm ischemia times and other risk factors are allowed and expected in this study. As noted above, the UNOS statistic upon which the OPG is based does not include deaths that are unrelated to graft failure, and the primary effectiveness endpoint will be defined similarly to the UNOS national statistics.

The formal statistical hypothesis test is as follows:

$$H_0: \pi_{OCS\ liver} \leq 0.765, \text{ and}$$

$$H_1: \pi_{OCS\ liver} > 0.765$$

where $\pi_{OCS\ liver}$ is the 6-month graft survival rate for organs preserved on the OCS Liver System.

The primary effectiveness endpoint will be summarized using counts and percentages and an exact 95% confidence interval for the true percentage based on the binomial distribution. The lower limit of confidence interval should be greater than 0.765 to reject the null hypothesis H_0 .

If any patient has missing 6-month graft survival in the end of study, the Kaplan-Meier estimates will be used to test null hypothesis. Subject not having 6-month graft survival will be censored at the date of last contact during the study. The lower limit of Kaplan-Meier estimates of 95% confidence interval at 6 months should be greater than 0.765 to reject the null hypothesis H_0 . Tipping point analysis will be provided for sensitivity analysis (Section 8.5).

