	
recipients of DCD livers is 88.5%, with an 12% margin to allow for the fact that extended warm ischemia times and other risk factors are allowed and expected in this study. As noted above, the UNOS statistic upon which the OPG is based does not include deaths that are unrelated to graft failure, and the primary effectiveness endpoint will be defined similarly to the UNOS national statistics.
 
The formal statistical hypothesis test is as follows:
 $H_0: \pi_{OCS\ liver} \leq 0.765, \text{ and}$ $H_1: \pi_{OCS\ liver} > 0.765$ 
where $\pi_{OCS\ liver}$ is the 6-month graft survival rate for organs preserved on the OCS Liver System.
 
The primary effectiveness endpoint will be summarized using counts and percentages and an exact 95% confidence interval for the true percentage based on the binomial distribution. The lower bound of confidence interval should be greater than 0.765 to reject the null hypothesis H_0.
 
If any patient has missing 6-month graft survival in the end of study, the Kaplan-Meier estimates will be used to test null hypothesis. Subject not having 6-month graft survival will be censored at the date of last contact during the study. The lower limit of Kaplan-Meier estimates of 95% confidence interval at 6 months should be greater than 0.765 to reject the null hypothesis H_0.
 
Each secondary effectiveness endpoint, except the rate of donor liver utilization after OCS perfusion, will be summarized using counts and percentages and an exact 95% confidence interval for the true percentage based on the binomial distribution. The secondary effectiveness endpoints will be analyzed using the PP and the mITT Populations. The rate of donor liver utilization after OCS perfusion will be summarized using counts and percentages and an exact 95% confidence interval for the true percentage based on the binomial distribution. This endpoint will be analyzed using the donor liver population.

Safety Analysis	
Safety will be analyzed principally by examination of the frequency of liver graft-related serious adverse events (LGRSAEs) up to the 30-day follow-up after transplantation.
 
This endpoint will be summarized using descriptive statistics. A 95% confidence interval for the mean based on the t-distribution will be presented.

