4.3. Trial Endpoints

4.3.1. Primary Effectiveness Endpoint

Liver graft survival through 6 months post-transplant, as defined per UNOS data collection criteria for graft status after liver transplantation*.

* If patient dies and the death was a result of some other factor unrelated to graft failure, the graft will be considered functioning not failed (see https://unos.org/wp-content/uploads/unos/Adult_TRF_Liver.pdf).

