8.5. Treatment of Missing Data

A tipping point analysis of the primary endpoint will be performed in the following manner for the PP population and mITT population. Initially the analysis will be performed with all missing values for the primary endpoint defined to be successes (i.e., not graft failures). If this analysis results in rejection of the null hypothesis, the analysis will continue by setting one missing value to be a graft failure and all of the other missing values to be successes. This procedure will continue in the same manner, each time setting one additional missing value to be a failure, until the first time that the analysis does not result in rejection of the null hypothesis. This point is referred to as the tipping point, the point at which conclusions change from being favorable to the treatment to being unfavorable.

No other data imputation is planned for effectiveness and safety measures.

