8.6. Sample Size Determination

Sample size calculations are based on the following specifications:

- Comparison to Objective Performance Goal (OPG)
- Endpoint is 6-month graft survival
- One-sided, exact binomial confidence interval
- Alpha = 0.025
- Power = 80%
- True proportion = 0.88
- Objective Performance Goal = 0.765.

Based on the above specifications, a sample size of 101 transplanted subjects with DCD donor liver preserved on OCS Liver System is required. The sample size will be increased to 130 to allow for a sufficient number of subjects in the per protocol population.

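### Does leaving the form of the Kaplan-Meier lower limit unnamed put the 0.025 level of the primary test at risk?

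*Combined protocol and SAP*

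**What the plan says.** Section 8.6 sizes the trial on a "One-sided, exact binomial confidence interval" at alpha 0.025 and 80% power, with "True proportion = 0.88" and "Objective Performance Goal = 0.765". That gives 101 subjects, raised to 130 to protect the size of the per-protocol population.

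Section 8.3.4.1 and the synopsis use the exact binomial 95% interval when every 6-month status is known. Otherwise the rule changes: "If any patient has missing 6-month graft survival in the end of study, the Kaplan-Meier estimates will be used to test null hypothesis". Patients without a 6-month status are censored at last contact, and the criterion becomes: "The lower limit of Kaplan-Meier estimates of 95% confidence interval at 6 months should be greater than 0.765". Neither place names a transformation or a variance formula.

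Section 8.1 names SAS as the software. Section 8.3 refers details of method to a SAP that "will be finalized prior to the database lock". Section 8.5 adds a tipping point analysis as a sensitivity check, which starts as follows: "Initially the analysis will be performed with all missing values for the primary endpoint defined to be successes". Under Section 4.3.1, when a patient dies of a cause unrelated to graft failure, "the graft will be considered functioning not failed".

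**The concern.** A single missing status moves the confirmatory decision from the exact method used for sizing to an interval whose form is not stated. Some common forms are more lenient than the exact limit. With plain or log limits the study could be declared positive at more than the stated 0.025.

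It could also pass a result that fails the most favourable step of the tipping point analysis. If every missing graft is set to success, nothing is missing, and on a natural reading the exact limit applies. That limit can fall below 0.765 while a plain Kaplan-Meier limit lies above it.

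Two features add to the worry. In a single-arm trial outcomes can be seen before the SAP is completed. The Kaplan-Meier sentences also do not repeat how grafts are carried after unrelated deaths.

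**Working it through.** **Inputs.** Performance goal 0.765, true survival 0.88, one-sided alpha 0.025, n = 101 and 130 (Section 8.6). The documents give no missing rate, so loss rates are assumed.

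**The plan's own figure.** At n = 101 the smallest count whose exact 95% lower limit exceeds 0.765 is 86 (limit 0.7669; 85 gives 0.7555). The binomial tail at 86 is 0.0226 if true survival is 0.765 and 0.850 if it is 0.88. Power stays at or above 80% from n = 101 on (checked to n = 139). The 101 is reproduced.

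**Formulas.** Let S be the Kaplan-Meier estimate and V the Greenwood sum of d/[r(r − d)], with d failures among r at risk. Without censoring V = (1 − S)/(nS). The lower limits are:

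- plain: S − 1.96·S·√V
- log: S·exp(−1.96·√V)
- log-log: S raised to the power exp(1.96·√V/|ln S|)

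**Worked case, 109 of 130.** S = 0.8385, V = 0.1615/(130 × 0.8385) = 0.001482, √V = 0.0385.

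- plain: 0.8385 − 1.96 × 0.8385 × 0.0385 = 0.7752, passes
- log: 0.8385 × exp(−0.0755) = 0.7775, passes
- log-log: exponent exp(0.0755/0.1762) = 1.535, limit 0.7631, fails
- exact: 0.7637, fails

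**Cut-offs and type I error in the limiting case of negligible censoring**

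| Form | Survivals needed, n = 101 (error) | Survivals needed, n = 130 (error) | Error range, n = 101-130 |
|---|---|---|---|
| Exact | 86 (2.3%) | 110 (1.6%) | 1.4-2.4% |
| Log-log | 86 (2.3%) | 110 (1.6%) | 1.3-2.4% |
| Plain | 85 (4.0%) | 108 (4.4%) | 3.0-5.0% |
| Log | 85 (4.0%) | 108 (4.4%) | 3.6-5.6% |

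Log-log has the same cut-off as exact at 28 of the 30 sizes. At n = 121 and n = 126 it needs one more survival. Plain and log need one or two fewer than exact at every size.

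**Rule as written.** The table overstates the risk, because with nothing missing the exact test applies. Simulating the actual rule (exact if none missing, otherwise Kaplan-Meier), with assumed uniform failure and loss times and an assumed 3% unrelated deaths kept as functioning, gives these type I errors:

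| Assumed loss | n | Plain | Log | Log-log |
|---|---|---|---|---|
| 0.5% | 101 | 2.9% | 2.9% | 1.9% |
| 0.5% | 130 | 2.4% | 2.8% | 1.5% |
| 1% | 101 | 3.6% | 3.6% | 1.8% |
| 1% | 130 | 3.1% | 3.8% | 1.7% |
| 2% | 101 | 4.0% | 4.2% | 1.7% |
| 2% | 130 | 3.2% | 4.2% | 1.7% |
| 5% | 101 | 4.3% | 5.0% | 1.8% |
| 5% | 130 | 3.9% | 4.5% | 2.0% |

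Monte Carlo error is about 0.1 point. At an assumed 0.1% loss, plain and log give 2.2% at n = 101 and 1.8-1.9% at n = 130, below 2.5%.

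**How often the switch occurs.** The chance of at least one missing status among 130 is 1 − (1 − q)^130: 12%, 48%, 73% and 93% for q = 0.1%, 0.5%, 1% and 2%.

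**One-loss example.** Take n = 130, 21 failures evenly spaced and one graft lost at mid-period. Plain (0.7743) and log (0.7766) pass; log-log (0.7622) fails. Setting the lost graft to success gives 109 of 130, where the exact limit of 0.7637 also fails. With log-log the primary test and the first tipping point step agree here.

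**Width of the disputed band.** At n = 130 with negligible censoring, plain or log change the decision only at 108 or 109 survivals. The probability of that is about 3% if true survival is 0.765 and 6% if it is 0.88.

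**The case for a change.** The strongest case for a change is that this is the confirmatory test, that an unstated default is not pre-specification, and that one sentence would close the matter. At 1% loss the switch occurs in most trials of 130, and plain or log limits then push the error of the whole rule to between 3% and 4%. If log-log is intended, saying so costs nothing.

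What stands is that the protocol does not name the form and that the form can decide a result near the boundary. The rest is weaker. Inflation needs both an unfavourable option that the plan never chooses and enough missing data. Section 6 lets graft status be obtained by telephone or from the medical record, and Appendix 1 allows one month either side of Month 6; both favour low missingness. Section 8.3 assigns method details to the SAP, and the transformation of a survival interval is such a detail. Nothing in the documents suggests that it would be chosen after looking at outcomes.

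The side points add little. Section 8.3.4.1 repeats the footnote on unrelated deaths in its own definition of the primary endpoint, so a Kaplan-Meier analysis of that endpoint carries those grafts as functioning. The conflict with the tipping point analysis rests on reading its first step as an exact test, which Section 8.5 does not state, and on the lenient forms.

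**Conclusion.** No change to the plan follows. The gap is real but is one that analysts fill sensibly. The log-log limit is in effect the Kaplan-Meier counterpart of the exact test used for sizing: the same cut-off at 28 of 30 sizes, and type I error of 1.5-2.0% under the rule as written at assumed losses of 0.5% to 5%. Its power at 0.88 is about 80-81% at n = 101 with 1% to 5% loss, with essentially no margin over the planned 80%, and about 91% at the planned 130 with 1% to 2% loss.

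Plain or log limits would give 2.4-5.0% over the same range, but no sentence in the plan calls for them. The software named is SAS, whose usual survival procedure is understood to report log-log limits unless told otherwise. The documents do not say this, so it is an assumption. It makes the log-log form the most natural outcome of following the plan. Without it, the choice still falls to the SAP, which Section 8.3 requires before lock.

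The conclusion assumes non-informative censoring and that the SAP settles the form in keeping with the 0.025 level. A SAP that specified plain or log limits would be a different finding.
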